### 3.0 STUDY DESIGN

#### 3.1 Overview

Our objectives will be met by performing two studies. The first is a 10-week, randomized, controlled, single-blinded, two-arm, parallel group, pilot trial at a single center and the second is a cross-sectional two-group comparative study.

Study I: A total of 40 persons with HIV may be screened and consented to identify the 32 participants to be enrolled and randomized into the pilot trial. These participants will be  $\geq 18$  years old, have been receiving antiretroviral therapy for at least three months with an HIV viral load  $< 75$  copies/mL, and have an ISI score  $\geq 11$ . These participants will be randomized 1:1 (stratified by age  $<40$  vs.  $\geq 40$  years) to either insomnia treatment with the SHUTi cognitive behavioral therapy program (N=16) or usual care (N=16).

Study II: The 32 participants with insomnia from Study 1 will then be compared to a similar group of 12 HIV-infected patients but with an ISI score  $< 11$ . Six will be  $<40$  years old and the other six will be  $\geq 40$  years old). Approximately 15 persons with HIV may be screened to identify this second group of 12 participants without insomnia.

#### 3.2 Eligibility Assessment

We will screen for insomnia using two methods. First, we currently screen for insomnia in the Eskenazi HIV clinics using the Insomnia Severity Index (ISI). As such, we will use these results to determine eligibility of these patients for either Study I or Study II. Patients will be asked in the clinic by our screeners if they wish to be contacted by our study personnel for study participation. If so, these patients will be referred to the study team. The patients' medical records will be reviewed so to determine their true eligibility. If found eligible for either Study I or Study II, then will then be contacted to schedule their Entry Visit. Second, we will do phone screening for insomnia using the ISI questionnaire for patients who either self-refer to Study I or who are referred by their HIV provider for Study I but who have not undergone in-person ISI screening in the clinics.

### 3.3 Study I Randomization

For those patients eligible for the pilot trial in Study I, they will be randomized at their Entry Visit. Randomization will be stratified by age (<40 years and  $\geq 40$  years). The randomization sequence will be placed in opaque envelopes that will only be opened and witnessed at the Entry Visit.

### 3.4 Entry Visit for both Study I and Study II

The Entry Visit will occur within 60 days of the routine clinic or phone ISI screening and HIV-1 RNA (viral load) testing that prompted referral to this study. This visit will occur at the Infectious Diseases Research Clinic located at the Fifth Third Office Building on the Eskenazi Hospital campus. After written, informed consent is provided by the participant, a random study code number will be assigned to the participant to ensure confidentiality. This study code number will be used for result reporting and data recording.

At this visit, medical records and current medications will be reviewed. Height, weight, and vital signs will be measured. All participants (both Study I and Study II) will complete the following surveys: ISI, PSQI, Generalized Anxiety Disorder-7 (GAD-7), PANAS (PANAS PA), SF-36, WHOQOL-HIV BREF, and CSRQ-25. All participants will begin the baseline sleep diary entries the night of the Entry Visit, which will be collected verbally over the phone 3 days later. In addition, information on alcohol use, tobacco use, and substance use will be solicited. These questionnaires will be administered in private with availability of the study team to assist only when asked by the participant. The participant may refuse to complete any of the questionnaires.

The participant will then perform the Digit Symbol Substitution Test, the FRAIL Index, and the Fried Index studies.

After these procedures are completed, participants in Study I will be randomized to either the SHUTi intervention or to Usual Care. For participants in Study II, study participation will be considered completed with no further follow-up.

Of note, study participants do not need to be fasting or refrain from smoking for any study visits in this protocol.

Participants who exhibit elevated depressive symptoms ( $\text{PHQ-9} \geq 10$ ) at the final study visit will be urged to follow-up with their primary HIV provider and/or clinical social worker regarding their depression. In addition, the study team will notify the primary HIV provider that his/her patient has completed participation in our trial and still has clinically elevated depressive symptoms. A list of local mental health service providers and clinics will be given to the patients' primary HIV providers or social workers.

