### 3.5 Week 10 Visit for Study I

The participant will come back to the Infectious Diseases Research Clinic for the Week 10 Study Visit. This visit will be scheduled between 63 and 84 days after the Entry Visit. The participant does not need to be fasting nor refrain from smoking at this study visit.

Weight and vital signs will be measured again. Participants will complete again the following surveys: ISI, PSQI, GAD-7, PANAS, SF-36, WHOQOL-HIV BREF, and CSRQ-25. Participants will begin the follow-up sleep diary entries the night of the 10 Week Visit, which will be collected verbally over the phone 3 days later. Questionnaires asking about personal alcohol, tobacco, and substance use will also be administered. These questionnaires will be administered in private with availability of the study team to assist only when asked by the participant. The participant may refuse to complete any of the questionnaires.

The frailty and cognitive function tests performed at the Entry Visit will not be repeated at the Week 10 Visit.

Participants who exhibit elevated depressive symptoms (PHQ-9  $\geq$  10) at this final study visit will be urged to follow-up with their primary HIV provider and/or clinical social worker regarding their depression. In addition, the study team will notify the primary HIV provider that his/her patient has completed participation in our trial and still has clinically elevated depressive symptoms. A list of local mental health service providers and clinics will be given to the patients' primary HIV providers or social workers.

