## 6.0 CLINICAL EVALUATIONS

### 6.1 Schedule of Events

Evaluation	Entry Visit for both Study I and Study II (within 90 days of last clinic-based ISI screening and HIV-1 RNA level assessment)	Weekly SHUTi Sessions for the intervention group in Study I (6 sessions in total)	Week 10 Visit for Study I (for both groups; 63-84 days after Entry Visit)
Informed Consent	X		
Documentation of HIV Status	X		
Medical/Psychiatric History	X		
Medication/Supplement Use History	X		
Diagnoses	X		X
Updated Psychiatric Treatment History			X
Updated Medications			X
Updated Diagnoses			X
Height	X		
Weight	X		X
Vital Signs	X		X
Laboratories obtained through routine clinical care	X		
Questionnaires: ISI, PSQI, PHQ-9, SF-36, WHOQOL-HIV, CSRQ-25, GAD-7, PANAS	X		X
Sleep History and Beliefs Survey (PRE-Treatment)	X		
Sleep History and Beliefs Survey (Post-Treatment)			X
Sleep Diary*	X*		X*
Alcohol, tobacco, substance use questionnaires	X		X
FRAIL Scale (frailty assessment)	X		
Fried Index (frailty assessment)	X		
SPPB Physical Functioning Assessment	X		
DSST Dementia Assessment	X		
Randomization for Study I participants	X		
SHUTi Intervention		X	

\*The study team will call the participant 3 days after the Entry Visit to verbally collect the participants first sleep diary. The study team will again call the participant 3 days after the Week 10 Visit to collect the second sleep diary.

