#### 6.2.6.6 Questionnaires

The ISI, PSQI, PHQ-9, SF-36, WHOQOL-HIV, PANAS, GAD-7, CSRQ-25, alcohol, tobacco, and substance use questionnaires (see Appendices) will be completed using online versions at both Study Visits in a quiet, private environment and assisted as needed by a trained member of the study team.

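### In Study I, a PHQ-9 total of 10 or more at the Entry Visit triggers no score-based action; the protocol's only total-score rule waits for the final visit, 63 to 84 days later

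*Combined protocol and SAP*

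**What the plan says.** The Schedule of Events (Section 6.1) has a row "Questionnaires: ISI, PSQI, PHQ-9, SF-36, WHOQOL-HIV, CSRQ-25, GAD-7, PANAS" marked at both Entry and Week 10. Section 6.2.6.6 says that these questionnaires "will be completed using online versions at both Study Visits in a quiet, private environment". The narrative survey lists in Section 3.4 (Entry Visit) and Section 3.5 leave the PHQ-9 out, although both sections then use a PHQ-9 threshold.

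The only action on the total score appears twice. In Section 3.4 (Entry Visit), participants scoring 10 or more "at the final study visit will be urged to follow-up with their primary HIV provider and/or clinical social worker regarding their depression". In Section 3.5, those above the same threshold "at this final study visit will be urged to follow-up with their primary HIV provider". Both add notice to the HIV provider and a list of local mental health services. The notice says that the patient has finished the trial and that symptoms remain elevated.

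For Study I the final visit is Week 10: "This visit will be scheduled between 63 and 84 days after the Entry Visit". For the comparison group, Section 3.4 (Entry Visit) says: "For participants in Study II, study participation will be considered completed with no further follow-up".

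Depression is not exclusionary unless it prevents the study procedures (note to 4.2.12), and eligibility has no upper limit on the PHQ-9 total.

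**The concern.** The protocol sets its own standard: it treats a PHQ-9 total of 10 or more as clinically elevated and worth telling the HIV provider about. It admits people with depression and measures the score on the day of randomization. In Study I it then does nothing with that score until the trial ends for the participant, and at that point it uses the Week 10 score instead.

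A participant with a high total and no positive item 9 could therefore go 9 to 12 weeks with a flagged result that nobody is required to act on, or indefinitely if the Week 10 visit is missed. What is at stake is timely referral for a condition that the study has itself measured. The primary analysis is not affected.

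**Working it through.** **Inputs from the documents**
- Study I size: 32 randomized, 16 per arm (Section 3.1).
- Final-visit window: 63 to 84 days after Entry (Section 3.5).
- Expected dropout: 25%, leaving about 12 per arm (Section 9.2).
- Threshold: PHQ-9 total of 10 or more (Sections 3.4 Entry Visit and 3.5).
- Share of participants at or above the threshold at Entry: not given.

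**Reproducing the plan's figure.** 16 × (1 − 0.25) = 12 per arm, as Section 9.2 states.

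**Delay.** 63 / 7 = 9 weeks; 84 / 7 = 12 weeks.

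**Never reaching the rule.** 32 × 0.25 = 8. This is an upper figure, because it takes dropout to mean missing Week 10. Someone who stops SHUTi but attends Week 10 is still covered. It counts participants of any score.

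**Which provisions act on the Entry total in Study I?**
- Item 9 procedure (Section 7.0, Section 10.3.2.3 and the Suicide Management Plan): triggered by item 9 or a spontaneous report. It does not use the total.
- Usual Care advice to see a primary care or HIV provider (Section 3.4.2): given to the whole arm, whatever the score. It is not specific to depression and carries no provider notice or service list. The SHUTi arm has no equivalent.
- Day-3 sleep-diary call (Sections 6.1 and 6.2.6.8): collects the diary.
- SHUTi session contacts (Sections 3.4.1 and 5.1): scheduling, homework, technical help and questions.
- Caregiver involvement before approach (Section 10.3.1) and withdrawal at a provider's request (Section 8.0): neither is tied to the score.

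None acts on the total.

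**Illustration under assumption.** Suppose 25% to 50% score 10 or more at Entry and dropout is unrelated to the score.
- At or above threshold: 32 × 0.25 = 8 to 32 × 0.50 = 16.
- Of these, missing Week 10: 8 × 0.25 = 2 to 16 × 0.25 = 4. The other 6 to 12 wait for Week 10, and some will have fallen below 10 by then and need the rule less.
- With 1:1 allocation, about half (4 to 8) are in Usual Care and already get the general advice. The other 4 to 8, in SHUTi, get neither the advice nor the score-based actions.

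**Possible effect of the fix on outcomes, under assumption.** Shift in the arm difference = p × d × e, where p is the share notified, d the between-arm difference in uptake of depression care, and e the effect of that care in scale points.
- Low: 0.25 × 0.10 × 2 = 0.05 points.
- High: 0.50 × 0.30 × 5 = 0.75 points.

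Higher uptake in Usual Care works against SHUTi; higher uptake in SHUTi reverses the sign. None of p, d or e comes from the documents.

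**The case against.** The strongest defence is that the rule is a deliberate end-of-study handover. It is tied to the final visit in both places, and the notice is worded for someone who has completed the trial. Prompting depression care at Entry could move the ISI and PHQ-9, which are 10-week outcomes in a 32-person pilot meant to produce usable effect sizes. Nothing in the documents requires an Entry trigger. All of that is fair, and it makes this a question of good practice, not of contradiction. It does not justify leaving a score that the protocol calls clinically elevated for 9 to 12 weeks. No reason for waiting is given, care is already unrestricted in Usual Care, and Section 9.2 does not expect significant differences.

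A second objection is that participants are not unprotected. That stands in part. A reader might infer that depressed Study I participants have no safeguard at Entry; the item 9 procedure and the Usual Care advice show otherwise. What Usual Care participants lack is depression-specific advice, provider notification and the service list. SHUTi participants lack these and the general advice as well.

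A reader might also infer that Study II participants are knowingly treated better. Study II has a single visit, so read literally the rule would apply to them at Entry, and its placement in a section covering both studies fits that reading. But no sentence says so, and the near-identical paragraph in Section 3.5 leaves open that the text was carried over. The gap in Study I does not depend on this comparison.

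**Conclusion.** The gap is real and modest. In Study I a PHQ-9 total of 10 or more at Entry leads to no score-based action; the rule comes 63 to 84 days later, and up to about 8 of 32 participants may never reach it. Those figures rest on the protocol's visit window and on its 25% dropout, read as missing Week 10.

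How many would be at or above the threshold at Entry cannot be derived from the documents. A reader might take the 8 to 16 of 32 shown above as a count of people left without help. It is not: it rests on an assumed 25% to 50% prevalence, and about half of those would be in Usual Care and already advised to see a provider.

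This is a participant-protection improvement. It does not invalidate the design, the sample size or the primary analysis.

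**What to change.** Keep the final-visit rule in both sections and add to Section 3.4 (Entry Visit) wording such as:

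> If a Study I participant's PHQ-9 total at Entry is 10 or higher, staff will, before opening the randomization envelope, advise the participant to contact the HIV provider and/or social worker about depression, inform that provider of the elevated score without disclosing the study arm, and supply the service list.

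Add the PHQ-9 to the survey lists in Sections 3.4 (Entry Visit) and 3.5 so that they match Sections 6.1 and 6.2.6.6. Report depression care started during follow-up by arm.

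The timing works. The questionnaires are completed online at the visit, a positive item 9 already stops the visit (Section 7.0), so answers have to be seen that day, and randomization comes last: "After these procedures are completed, participants in Study I will be randomized to either the SHUTi intervention or to Usual Care". Because the trigger precedes allocation, it cannot depend on arm.

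The cost is one sentence, two list corrections and one extra tabulation; no new assessment is needed. The delay falls to 0 days for everyone who completes the PHQ-9 at Entry. Those who decline remain uncovered, since "The participant may refuse to complete any of the questionnaires".

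The downside is that notification may prompt depression care before the Week 10 ISI and PHQ-9, and uptake may differ by arm, so a small shift either way is possible. Psychiatric treatment and medication changes are recorded at Week 10 (Sections 6.1 and 6.2.5), so care can be described by arm for those who attend. That describes any shift; it does not remove it.

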### 3.4 SHUTi Treatment Sessions and Usual Care

#### 3.4.1 SHUTi

SHUTi ([www.myshuti.com](http://www.myshuti.com)) is an evidence-based, cognitive-behavioral, online intervention for insomnia developed by our colleague and consultant, [name] (31). It is based on a well-established face-to-face CBT-I (27, 28). SHUTi consists of six, 40-minute, weekly sessions during which the intervention components of stimulus control, sleep restriction, sleep hygiene, cognitive restructuring, and relapse prevention are delivered. Each SHUTi session has the same structure: the main content, a homework screen with options, and a summary of the main points. The internet requirements are minimal, as SHUTi can run on a dial-up connection. The SHUTi program is currently being used in both research and clinical settings.

To minimize treatment barriers, attrition, and subject burden, the SHUTi treatment sessions will occur in private at [name] laboratory, the Infectious Diseases Research Clinic at Eskenazi Health Hospital, or a

location selected by the patient where s/he can access a computer with internet, such as the patient's home, the patient's work, a family member's/friend's home, or a public library. The location will be chosen by the participant. To help maintain privacy, patients will be provided with ear bud headphones if they plan to complete SHUTi sessions at remote locations and do not already own a pair of headphones that they would rather use. We will also tell patients that, if they choose to complete SHUTi session where others are present, these other people (e.g., family member or friend) may realize that they are completing a treatment for insomnia. It will be up to each patient to decide if the available remote locations provide sufficient privacy. Up to 6 sessions will be performed between the Entry Visit and the Week 10 Visit. No physiologic or biologic assessments will be performed during these sessions. The participants need not be fasting for these sessions.

At each in-person SHUTi session, a research assistant trained in the use of this intervention will first collect homework and will start the appropriate session on a computer. The patient will then work through the session alone at his/her own pace. At the end of the session, the research assistant will give the patient the printed homework assignment and will schedule the next session.

Remote SHUTi sessions will be scheduled just like in-person sessions. Patients who select the remote treatment option will complete the first SHUTi session in person, at which time they will be given a SHUTi binder with printouts of all future homeworks. To begin each remote SHUTi session, an assistant will call the patient to instruct the patient to put last week's homework in the SHUTi binder, to address any technical issues, and to ensure that the patient has launched the correct SHUTi session for that day. The patient will then work alone through the SHUTi session at his/her own pace, with the assistant monitoring progress remotely on the secure SHUTi website set up for this trial. To end the session, the assistant will call the patient back to address any questions and ensure that the patient has identified the correct printed homework in the SHUTi binder.

Information is collected by the SHUTi program while it is being used by participants, which the program requires to tailor interventions to each participant's particular sleep problem. Of note, participants in our trial will not enter any identifying information into the SHUTi program. Instead, they will only enter information related to their current sleep problem (sleep diary, insomnia symptoms, and treatment goals) and will only be identified by a unique study ID number and a password provided by our team. Thus, the data entered into SHUTi will remain anonymous. The key linking participant names with their SHUTi login information will be kept in a separate secure and locked file cabinet. All data collected through SHUTi will be saved on password-protected computers and secure servers.

### 3.4.2 Usual Care

Patients randomized to the Usual Care group will be encouraged to follow-up with their primary care or HIV provider. There will be no formal interaction with the participants between the Entry Visit and the Week 10 Visit. However, the participants will be encouraged to contact the study team for any changes in their condition. There will be no restrictions on the care that can be received, although we will assess changes in care during the trial.

### 3.5 Week 10 Visit for Study I

The participant will come back to the Infectious Diseases Research Clinic for the Week 10 Study Visit. This visit will be scheduled between 63 and 84 days after the Entry Visit. The participant does not need to be fasting nor refrain from smoking at this study visit.

Weight and vital signs will be measured again. Participants will complete again the following surveys: ISI, PSQI, GAD-7, PANAS, SF-36, WHOQOL-HIV BREF, and CSRQ-25. Participants will begin the follow-up sleep diary entries the night of the 10 Week Visit, which will be collected verbally over the phone 3 days later. Questionnaires asking about personal alcohol, tobacco, and substance use will also be administered. These questionnaires will be administered in private with availability of the study team to assist only when asked by the participant. The participant may refuse to complete any of the questionnaires.

The frailty and cognitive function tests performed at the Entry Visit will not be repeated at the Week 10 Visit.

Participants who exhibit elevated depressive symptoms (PHQ-9  $\geq$  10) at this final study visit will be urged to follow-up with their primary HIV provider and/or clinical social worker regarding their depression. In addition, the study team will notify the primary HIV provider that his/her patient has completed participation in our trial and still has clinically elevated depressive symptoms. A list of local mental health service providers and clinics will be given to the patients' primary HIV providers or social workers.

### 3.6 Study Duration and Participant Retention

The maximum study period for each Study I participant will be preferably 10 weeks but at most 12 weeks (if the participant requires extra time to schedule the Week 24 visit). In order to promote retention in the study, the participant participants will be financially compensated at each visit.

## 4.0 SELECTION AND ENROLLMENT CRITERIA FOR BOTH STUDY I AND STUDY II

### 4.1 Inclusion Criteria

- 4.1.1 HIV-1 infection, documented by both: (1) any licensed rapid HIV test or HIV enzyme test kit at any time prior to study entry and (2) by at least one detectable HIV-1 antigen or at least one detectable plasma HIV-1 RNA viral load.
- 4.1.2 Age equal to or greater than 18 years.
- 4.1.3 Ongoing receipt of stable antiretroviral therapy of any kind for at least 3 months prior to the Entry Visit.
- 4.1.4 HIV-1 RNA level  $<$  75 copies/mL obtained during routine clinical care within 90 days of the Entry Visit.

NOTE: There are no CD4 cell count eligibility criteria for this trial.

- 4.1.5 ISI score  $\geq$  11 for Study I and ISI score  $<$  11 for Study II

